11.1 General Provisions

A multicenter controlled comparative prospective cohort study is planned.

It is known that chronic aortic valve insufficiency leads to significant remodeling of the left ventricle and development of functional mitral regurgitation. On one hand, residual mitral regurgitation may complicate the postoperative period by increasing the preload on the left ventricle; however, a dilated left ventricle after surgical correction of the aortic defect still requires supraphysiological preload during the most vulnerable period of early rehabilitation. As the volume of the left ventricle regresses, functional mitral regurgitation is also capable of regressing. A significant scientific task is to address the role of functional mitral regurgitation in the reverse remodeling of the left ventricle after correction of chronic aortic valve insufficiency.

11.2 Definition of the study group

Patients who have undergone open surgical correction of aortic valve insufficiency with large eccentric left ventricle remodeling (EDV more than 250 ml). Men and women over 18 years old.

11.2.1 Inclusion Criteria

Potential study subjects must meet the following criteria:

1. *Age over 18 years*
2. *Planned primary elective surgery for chronic aortic regurgitation*
3. *Presence of functional mitral regurgitation*
4. *Left Ventricular End-Diastolic Volume ≥ 250 ml*

11.2.2 Non-inclusion Criteria

1. *Infectious endocarditis*
2. *Previous myocardial infarction*
3. *Necessity of simultaneous myocardial revascularization*
4. *Acute aortic valve insufficiency of any etiology*
5. *Previously established left ventricular dilation not associated with the development of aortic regurgitation*
6. *Permanent or persistent form of atrial fibrillation*

[figure not shown]
7. *Ongoing pregnancy within the first 12 months after surgery*
8. *Simultaneous participation in other studies*
9. *Implanted heart pacemaker*
10. *Refusal to sign informed consent*

During the population analysis, the research team reserves the right to add new exclusion criteria if required to achieve sample representativeness, due to the clinical situation, or common sense.

11.2.3 Exclusion Criteria

1. *Acute coronary event diagnosed within 12 months after surgical correction of the aortic defect.*
2. *Need for resynchronization therapy or permanent right ventricular pacing in the first 12 months after surgery.*
3. *Re-do cardiac surgery for any reason within 12 months after the operation.*

Figure 1. 'Principle scheme of forming the study working sample'

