7. PROTOCOL SYNOPSIS

Study Title	Assessment of the left ventricle reverse remodeling outcomes in patients with aortic valve insufficiency after surgical correction
Sponsor	Investigator-Initiated Study
Study Phase	Phase III
Hypothesis	We hypothesize that surgical correction of functional mitral regurgitation during interventions for chronic aortic valve insufficiency in patients with significant dilatation of the left heart chambers affects the reverse remodeling of the left ventricle in the postoperative period.

Research objectives and tasks	
Research objective:
 
To assess myocardial reverse remodeling in patients with significant left ventricular dilation caused by chronic aortic regurgitation, depending on the degree of mitral valve insufficiency and surgical approach.
 
Main objectives of the study:
 
1. To evaluate the short-term and long-term outcomes of aortic valve replacement for aortic valve insufficiency in patients with significant left ventricular dilation2. To compare the results of myocardial reverse remodeling depending on the strategy regarding functional mitral valve insufficiency at 3 and 12 months post-surgery3. To determine preoperative predictors of an unfavorable left ventricle function and architecture recovery prognosis.4. Assess the patients life quality 12 months after surgery5. Develop a clinical protocol for simultaneous surgical treatment of mitral regurgitation during aortic valve replacement in patients with significant left ventricular myocardial remodeling caused by chronic aortic regurgitation
Study design	This study is a multicenter, comparative, prospective

Inclusion criteria	
1. Age over 18 years2. Proposed primary elective surgical intervention for chronic aortic regurgitation3. Presence of functional mitral regurgitation4. Left Ventricular End-Diastolic Volume 250 ml\geq
Exclusion criteria	
1. Infectious endocarditis2. Previous myocardial infarction3. Necessity for simultaneous myocardial revascularization4. Acute aortic regurgitation5. Previously established left ventricular dilation not associated with the development of aortic regurgitation6. Lack of informed consent
Number of study subjects	120 patients

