Investigated procedure	
It is planned to study the initial and long-term results of left ventricle reverse remodeling in patients with aortic regurgitation, depending on the strategy chosen for the correction of functional mitral regurgitation and its severity.

Duration of observation	12 months after surgical treatment
Methods of statistical evaluation	
The determination of the significance of differences between quantitative data of unrelated samples will be carried out using the Student's t-test under the condition of normal distribution; in the case of non-normal distribution, the Mann-Whitney test, White's test, Van der Waerden test, and Kolmogorov-Smirnov test are planned to be used. In the case of analyzing the significance of differences in quantitative data in related samples with a normal distribution, the paired Student's t-test is planned to be used; in the case of non-normal distribution, the Wilcoxon test and sign test will be used. Qualitative data analysis will be performed using the χ^2 test and the McNemar test. To assess the reliability of the relationship between quantitative data, regression analysis, Pearson's correlation coefficient, Spearman's rank correlation coefficient, and Kendall's correlation coefficient are planned to be used. Descriptive and analytical statistical methods will be finalized after analyzing the sample size. To eliminate the influence of differences in baseline clinical parameters on the study outcome, a propensity score matching analysis (PSM) is planned between the ordinary 'Unmatched' groups using the nearest neighbor matching method for 1:1 pair matching.
 
Demographic data and clinical indicators will be presented using descriptive statistics (absolute indicators and percentage shares for categorical variables, or mean \pm standard deviation for normally distributed continuous variables; for continuous variables with non-normal distribution, the median and interquartile range will be specified). The significance of differences in repeated measurements will be analyzed using ANOVA.

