10.2 Study endpoints

Primary endpoints:

1. *Reduction of the left ventricle end-diastolic volume at 3 and 12 months after surgical correction of aortic regurgitation*
2. *Freedom from readmission for heart failure related conditions 12 months after surgery*

Secondary endpoints:

1. Patient quality of life according to the EQ-5D-5L questionnaire results.

Exploratory endpoints:

1. Left ventricle ejection fraction at 3 and 12 months after surgical correction of aortic regurgitation

2. Diastolic function of the left ventricle based on echocardiography results, assessed preoperatively and at 3 and 12 months after surgical correction of the aortic regurgitation (mean E/e', DT)
3. Indexed to BSA volume of the left atrium (according to transthoracic echocardiography results) preoperatively, as well as at 3 and 12 months after surgical treatment

*BSA – body surface area, calculated using the Mosteller formula

11. Study design

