12.1 Preliminary Screening (Visit 0)

As part of the clinical work at the Petrovsky NRCS and BUZ VO VOKB No. 1, a screening of the medical documentation of patients scheduled for surgical treatment for aortic valve insufficiency will be conducted. Subjects who meet the inclusion criteria and do not have any exclusion criteria will be offered participation in the study.

Patients may also be initially referred by other specialists from other medical institutions for planned surgical treatment of chronic aortic regurgitation.

Subjects who express interest in participating in the study will be invited to Examination 1.

During Examination 1, patients will be offered an informational brochure, developed by the research team in collaboration with the Petrovsky NRCS research development department (print run of 200 copies), containing comprehensive information revealing the potential benefits and risks of participating in the study. After reviewing the information and having all relevant clarifying questions answered by the researcher, the subject will be given sufficient time to sign the voluntary informed consent. Voluntary informed consent must be obtained exclusively by a specialist qualified as a cardiologist or cardiovascular surgeon. Prior to obtaining voluntary informed consent, it is not possible to carry out any of the procedures provided for in this study.

Examination 2 is carried out on the 2nd day after surgical treatment of aortic valve insufficiency in the intensive care unit before leaving for the specialized department intensive care unit.

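### Section 11.2.3 excludes enrolled, operated patients for events in the 12 months after surgery; if they leave the analysed sample, both primary comparisons rest on a post-operative selection that baseline matching does not correct.

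*Protocol*

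**What the plan says.** Protocol Section 11.2.2 lists non-inclusion criteria, which apply at entry. Section 11.2.3 is a separate list headed as exclusion criteria, with three items:

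- "Acute coronary event diagnosed within 12 months after surgical correction of the aortic defect"
- "Need for resynchronization therapy or permanent right ventricular pacing in the first 12 months after surgery"
- "Re-do cardiac surgery for any reason within 12 months after the operation"

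The caption of Figure 1, which follows this list, describes a scheme for how the working sample is formed. The figure itself is not shown.

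Patients are screened while they await surgery and consent at Examination 1 (Sections 12.1 and 18.3), so the three items can apply only to people already enrolled and operated on.

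Section 10.2 gives two primary endpoints: "Reduction of the left ventricle end-diastolic volume at 3 and 12 months after surgical correction of aortic regurgitation" and "Freedom from readmission for heart failure related conditions 12 months after surgery".

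Section 11.1 describes a prospective comparative cohort. The control for group differences that the synopsis names is 1:1 nearest-neighbour propensity matching, whose stated purpose is "To eliminate the influence of differences in baseline clinical parameters on the study outcome".

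Section 11.2.2 also lets the research team add exclusion criteria while the population is being analysed. Sections 15 and 15.1 require agreement of the principal investigator and the ethics committee for protocol changes, but do not say that this must precede knowledge of outcomes.

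**The concern.** The three events fall between the start of follow-up and the primary outcome. Re-operation for any reason would include re-operation on a mitral valve that was left alone or repaired. Pacing or resynchronisation may also follow from the operation performed or from a ventricle that fails to recover. An acute coronary event is the least likely of the three to depend on strategy.

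If such patients are dropped, each strategy is judged on the patients who avoided these events. A strategy that produces more re-operations or device implants then loses more of its poor results and looks better than it is. The readmission endpoint is exposed in the same way: a patient readmitted for heart failure who later needs resynchronisation or re-operation could leave the comparison together with that readmission. If exclusion reaches back over all visits, a patient with an event after month 3 would also lose a valid 3-month volume.

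Matching makes the groups alike before surgery. It does not undo selection on what happened after surgery, and enrolling more patients does not shrink this kind of error.

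**Working it through.** **1. Timing.** Enrolment precedes surgery. The exclusion window is 0 to 12 months after surgery. Volumes are measured at 3 and 12 months, and readmission is counted to 12 months. The exclusion window therefore covers the follow-up of both primary endpoints.

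**2. The protocol's own sample-size figure.** The synopsis gives 15 ml/m², 80% power, 5% alpha and at least 64 per group, but no SD. For a two-sided two-sample t-test, 64 per group gives a detectable standardised difference of 0.499, so the implied SD is 15 / 0.499 = 30.06, about 30 ml/m². This refers to the indexed 12-month volume. The Section 10.2 endpoint is a reduction in volume with no indexing stated, so the volume figures below are a guide to scale only.

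**3. Volume (illustration; removal shares and correlation are assumed).** Let removal occur when a latent normal score, correlated ρ with poor remodelling, exceeds its upper f quantile z. With no true strategy effect, the mean of those kept moves by

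shift(f) = ρ × SD × φ(z) / (1 − f).

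With ρ = 0.5 and SD = 30:

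- f = 2%: 15 × 0.0484 / 0.98 = 0.74
- f = 5%: 15 × 0.1031 / 0.95 = 1.63
- f = 10%: 15 × 0.1755 / 0.90 = 2.92

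| Removed, group A vs B | False difference, ml/m² | Share of 15 ml/m² |
|---|---|---|
| 5% vs 2% | 1.63 − 0.74 = 0.89 | 6% |
| 5% vs 0% | 1.63 | 11% |
| 10% vs 2% | 2.92 − 0.74 = 2.18 | 15% |

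At ρ = 0.5 and 5% removed, removed patients are worse than kept ones by 15 × 0.1031 × (1/0.05 + 1/0.95) = 32.6 ml/m². At ρ = 0.25 every shift halves. At ρ = 0, or with removal equal in rate and kind in both groups, the shift is zero.

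Standard error of the difference: 30 × √(2/64) = 5.3 ml/m²; with the planned 120 split equally, 30 × √(2/60) = 5.5 ml/m². Every shift in the table is below one standard error.

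**4. Does balancing baseline remove it?** In a simulation with 2 million patients per scenario, no strategy effect and fine stratification on the baseline covariate in place of matching, the difference on all operated patients was about 0 (at most 0.1 ml/m²). After exclusions that depended on strategy and post-operative course it was −0.6, −1.4 and −2.2 ml/m² with 16%, 22% and 31% removed in one group against 9% in the other. It stayed at about 0 when strategy did not affect exclusion given baseline.

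**5. Readmission (illustration; all risks assumed).** With true risk p = 15% in both groups and risk q among those removed, the risk among those kept is (p − f × q) / (1 − f).

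| Removed | q = 30% | q = 50% |
|---|---|---|
| 5% vs 0% | 14.21% vs 15.00%: 0.8 points | 13.16% vs 15.00%: 1.8 points |
| 10% vs 2% | 13.33% vs 14.69%: 1.4 points | 11.11% vs 14.29%: 3.2 points |

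Standard error at 60 per group: √(2 × 0.15 × 0.85 / 60) = 6.5 points.

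**6. Precision.** At a standardised difference of 15/30 = 0.5, power is 80.1% with 64 per group, 78.2% with 61 (5% removed) and 76.1% with 58 (10% removed).

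**The case against.** The strongest reply is that Section 11.2.3 gives only a heading and three bullets. It does not say whether an excluded patient leaves follow-up, one endpoint or every analysis, or whether data already collected are kept. A SAP that is not shown could define a fuller analysis set. This stands in part, and the point is conditional for that reason. It does not clear the rule: the criteria are stated, they are set apart from the entry criteria, and the figure caption ties them to forming the sample. A SAP that kept these patients in the analysis would conflict with Section 11.2.3 read in that way.

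A second reply is that the investigators may want remodelling without later device therapy or re-operation. Section 11.2.2 already bars an implanted pacemaker at entry. That is a legitimate question, but deleting patients who had the events does not answer it, because those left need not be comparable between strategies.

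Third, the illustrated shifts are below one standard error. This is true and limits how strongly the point can be put.

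Two stronger readings are tempting. A reader might infer that the synopsis and Section 12.1 contradict Section 11.2.3, because the synopsis exclusion list has none of the three events and screening is to offer participation to those without any exclusion criterion. The documents do not support that: the synopsis list corresponds to the entry criteria of Section 11.2.2 in abridged form, and the screening sentence is naturally read the same way. A reader might also infer that outcome data are certainly discarded; the text does not say so.

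**Conclusion.** The point holds in conditional form. If patients meeting Section 11.2.3 leave the analysed sample, both primary comparisons are conditioned on post-operative events that may depend on mitral strategy and on poor remodelling, and the planned matching does not correct this.

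The protocol gives no event rates, so neither size nor direction can be computed, and the bias may be zero. With 5% to 10% removed in one group and 0% to 2% in the other, latent correlation 0.5 and SD 30 ml/m², the volume contrast shifts by about 0.9 to 2.2 ml/m², or 6% to 15% of the 15 ml/m² target. The readmission contrast shifts by about 0.8 to 3.2 percentage points under the assumed risks. Both are below one standard error, so it would be wrong to infer that the rule must overturn the result. It should be fixed because the distortion is systematic and avoidable, and because 12-month outcomes of patients who leave follow-up may not be recoverable later.

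**What to change.** Amend the protocol so that:

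1. The primary analysis population is defined by baseline criteria only.
2. The three events in Section 11.2.3 are recorded as outcomes and reported by mitral strategy.
3. Patients who have them stay in follow-up and in the primary analysis, with all available 3- and 12-month volumes and all heart-failure readmissions.
4. The set restricted by the present Section 11.2.3 is reported as a sensitivity analysis, with the number removed per strategy.
5. Any exclusion criterion added under Section 11.2.2 comes by approved amendment and applies only to patients enrolled afterwards.

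The cost is one amendment. Table 1 already schedules echocardiography and complication assessment at 3 and 12 months. If excluded patients would otherwise have left follow-up, retaining an assumed 5% to 10% of 120 means 6 to 12 patients and at most 12 to 24 visits at Examinations 4 and 5, all within the schedule planned for 120.

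The downside is a change in what is estimated. The primary comparison would include the effect of later re-operation or device therapy, with some added variability. The sensitivity analysis would show how far the result depends on that choice.

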12. ASSESSMENT METHODS AND PROCEDURES

An informed consent will be obtained from each subject prior to conducting any procedure related to the protocol of this study.

12.1 Preliminary Screening (Visit 0)

As part of the clinical work at the Petrovsky NRCS and BUZ VO VOKB No. 1, a screening of the medical documentation of patients scheduled for surgical treatment for aortic valve insufficiency will be conducted. Subjects who meet the inclusion criteria and do not have any exclusion criteria will be offered participation in the study.

Patients may also be initially referred by other specialists from other medical institutions for planned surgical treatment of chronic aortic regurgitation.

Subjects who express interest in participating in the study will be invited to Examination 1.

During Examination 1, patients will be offered an informational brochure, developed by the research team in collaboration with the Petrovsky NRCS research development department (print run of 200 copies), containing comprehensive information revealing the potential benefits and risks of participating in the study. After reviewing the information and having all relevant clarifying questions answered by the researcher, the subject will be given sufficient time to sign the voluntary informed consent. Voluntary informed consent must be obtained exclusively by a specialist qualified as a cardiologist or cardiovascular surgeon. Prior to obtaining voluntary informed consent, it is not possible to carry out any of the procedures provided for in this study.

Examination 2 is carried out on the 2nd day after surgical treatment of aortic valve insufficiency in the intensive care unit before leaving for the specialized department intensive care unit.

12.2 Early postoperative examination (Examination 2)

An assessment of the surgical treatment initial results will be conducted: stability of the pre-perfusion period, dosage of perioperative pharmacological support medications, features of the surgical intervention, and indicators of the body's internal environment. Mandatory study – transthoracic or transesophageal ECHO-cardiography.

12.3 Assessment 9-14 days after surgery (Examination 3)

A comprehensive assessment of the inpatient treatment stage is planned, according to Table 1.

12.4 First outpatient visit (Examination 4)

Routine registration of parameters reflecting the rate of reverse remodeling of the left ventricle, associated parameters, patient life quality, and analysis of adverse events occurring from Examination 3 to Examination 4 is planned.

In the event that the patient cannot or does not wish to attend the examination, comprehensive information and task resolution will be conducted by phone. If the visit is postponed for any reason, the schedule of subsequent examinations will not be modified.

**Table 1. Procedures provided by the study protocol**

Examination Number	0	1	2	3	4	5
Planned activities	Screening	Inclusion in the study	ICU	11 days	3 months	12 months (EOS)
				± 2 days	± 7 days	± 14 days
Assessment of eligibility for study participation	x					
Familiarization with the conditions of participation in the study and possible risks		x				
Signing the informed consent		x				
Medical history collection		x				
General clinical evaluation		x	x	x	x	x
Anthropometry (height without shoes and weight in light clothing)		x			x	x
ECHO-cardiography		x	x	x	x	x
Questionnaire completion		x		x	x	x
6-minute walk test		x		x	x	x
ECG		x	x	x	x	x
Assessment of complications since the previous examination			x	x	x	x
NT-proBNP (optional)		x			x	x
Myocardial MRI with gadolinium contrast enhancement (optional)		x				x

12.4 Outcome assessment

12.4.1 History taking

Detailed recording of medical history and life history is planned during Examination 1.

12.4.2 Demographic data

The date of birth and gender of each study participant will be entered into the database during Examination 1.

12.4.3 Objective examination

A standard clinical examination is provided as part of Examinations 1-5.

12.4.4 Height and weight

Height in centimeters and weight in kilograms will be assessed during Examinations 1, 4, 5. Body weight will be recorded to the nearest 0.1 kilogram [kg] in light clothing without shoes. Height will be recorded to the nearest 1 cm without shoes.

12.4.5 Electrocardiography (ECG)

A standard 12-lead ECG (after 5 minutes of rest) will be performed (at Examination 1 (baseline), examinations 3, 4, 5 according to the standard method (paper speed 50 mm/sec, amplitude 10 mm/mV, with at least 5 seconds of recording available for each lead). Recording will be conducted using an automatic recorder with digital signal processing capability. Heart rate will be assessed, and potential disturbances in heart rhythm, conduction, and repolarization parameters, such as QT interval prolongation or atrioventricular block, will be recorded.

